#### **2.4 Framework**

Primary and secondary comparative objectives of phase II part of DIVE-1 trial are tested for superiority in favour of intervention versus control treatment period. For phase I study, none statistical tests will be done and only descriptive analysis with go no go rule for safety will be done. For long term follow-up phase, intra-patient comparisons will be done to assess the maintenance efficacy and safety.

#### **2.5 Statistical interim analyses and stopping guidance**

No statistical interim analysis was planned. Stopping guidance for safety (go no go rule with evaluation by an independent Monitoring Committee) is detailed in study protocol and in section 2.1.

#### **2.6 Timing of analysis**

Final analysis for phase II is planned to take place in June 2024 after the database is cleaned and locked according to data management plan. The first main report/publication of the DIVE-1 trial will be prepared at the same time.

#### **2.7 Timing of outcome assessments**

The time points at which outcomes are measured is provided in table 1. Full detail of the schedule of the study visits are described within the clinical trial protocol.

**Table 1. The schedule of follow-up study visits**

	SC	Baseline	Implantation /titration	V1 (randomization phase II)	V2	V3	V4	Visites at long term every 6 months (1)
Possible delay	/	+2 weeks	+1 months	+1 week	+1 week	+1 week	+1 week	+/- 2 weeks
Checking inclusion and non-inclusion criteria	x							
Informing the patient	x							
Signing of consent	x							
Randomisation		x		x				
Socio-demographic data (age, socio-cultural level), previous and current associated medical and psychiatric disorders	x							
Medical check-up	x	x	x	x	x	x	x	x
Clinical examination								
Weight, height, BP with orthostatic hypotension test, ECG, temperature, respiratory rate	x	x	x	x	x	x	x	x
Collection of concomitant treatments	x	x	x	x	x	x	x	x
Psychiatric assessment		x		x	x	x		x
Chest X-ray, cardiac ultrasound		x						
Covid-19 test before surgery (if required by Covid-19 pandemic health measures)		x						
Implantation neurosurgical procedure			x					
Post-operative CT scan			x					
Monitoring of therapeutic adaptation (in hospital and then at home by daily calls)			x					
Standard biological work-up		x	x	x	x	x	x	x
FSH and LH tests (for all women)								
β-HCG assay (for women of childbearing age only)		x	x	x	x	x	x	
Continuous actimetry measurement (PKG)				x	x	x	x	
Acute L-dopa administration test (MDS UPDRS part III, video dyskinesia scales)	x							
MDS UPDRS part III, video dyskinesia scales in On Drug condition (either oral L-dopa or brain dopamine)				x	x	x	x	x
MDS-UPDRS parts I, II and IV		x		x	x			x
MOCA				x	x	x	x	x
Neuropsychological examination (cognition and behaviour) : NPI, PAS, LARS, ECMP	x			x	x	x	x	x
Clinical Global Impression (CGI) physician	x			x	x	x	x	x
Auto-questionnaires : CGI patient, échelle de Schwab et England, échelle d'Epworth, de Parkinson's Disease Sleep Scale, PDQ39	x			x	x			x
patient diary (periods 1 et 2)				x	x	x	x	x
Brain MRI		x				x	x	

	SC	Baseline	Implantation /titration	V1 (randomization phase II)	V2	V3	V4	Visites at long term every 6 months (1)
Possible delay	/	+2 weeks	+1 months	+1 week	+1 week	+1 week	+1 week	+/- 2 weeks
Exploratory criteria: pharmacogenetic and biobanking		X						
Exploratory criteria: Biology (oxidised metabolites of dopamine)		X	X		X	X	X	
Adverse events	X	X	X	X	X	X	X	X

### **3 STATISTICAL PRINCIPLES**

#### **3.1 Confidence intervals and p-values**

All applicable statistical tests will be 2-sided and will be performed using a 5% significance level.

No statistical comparisons will be done for secondary objectives, only a descriptive analysis will be performed and we will report standardized differences between active and control period as effect sizes.

All confidence intervals (CIs) presented will be 95%CI and 2-sided.

#### **3.2 Adherence and Protocol Deviations**

Patient's adherence during phase II part was evaluated by the volume of ICV Dopamine (placebo) before each refill and compared to the planned volume. For the oral L-dopa regimen, the adherence will be evaluated by the judgment of clinician regarding the optimized dose. Deviation in adherence will be defined as a one ml difference for ICV Dopamine (placebo) and as a modification of more than 20% of planned dose for the oral L-dopa regimen.

Protocol deviations will be identified and classified as major or minor in blind reviews before the database freezing. Major deviations will include unexpected treatment modification (dose, duration) of dopamine or oral treatment. The number and % of patients with major and minor protocol deviations will be provided, with details of the type of deviation. No formal statistical comparison will be done.

#### **3.3 Analysis population**

For phase I study, all included patients who have been operated, whatever they received or not a dose of study treatment, will be considered in analysis as a safety population.

For the phase II study, regarding the proof of concept, the efficacy population will include all randomized patients, who completed the two-treatment period with available primary endpoint —and without major protocol deviation. All patients randomized and excluded from the efficacy population will be described with the reason of exclusion. The safety population of phase II study will include all randomized patients who receive ICV dopamine (or placebo).

For the long-term phase part of study, all patients having received ICV dopamine for at least 6 months after end of the phase II part will included in the analysis population of long-term phase part of DIVE-1 study.

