***Primary outcome:***

A case-report descriptive analysis will be done by reporting individual values of primary outcome according to the two periods as well as by using spaghetti plots showing the individual change from control to experimental period (by indicating the sequence of treatment). We also reported the mean, median and range values for control and experimental period. To assess the treatment effect (experimental vs. standard treatment) on primary outcome, we will use a Wilcoxon 'signed rank test. We will also report the standardized differences (Hedges'g) calculated from the within-patient's differences (E1-S2 and E2-S1) as effect size (calculated on rank transformed data).

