### **5.4 Missing data**

No imputation, only cases available analysis will be done.

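### The only phase II superiority test is run on completers without major deviation, so treatment failures can leave it in either direction, and no efficacy analysis brings them back

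*SAP*

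**What the plan says.** - **Population.** SAP section 3.3 defines the phase II set for efficacy: "the efficacy population will include all randomized patients, who completed the two-treatment period with available primary endpoint", and then "and without major protocol deviation". It gives the proof-of-concept purpose as the reason. Excluded patients are to be described with the reason, and all randomised patients who received ICV dopamine or placebo stay in the safety population.
- **What excludes.** Section 3.2: "Major deviations will include unexpected treatment modification (dose, duration) of dopamine or oral treatment". On who decides: "Protocol deviations will be identified and classified as major or minor in blind reviews before the database freezing".
- **The test.** Section 2.4 says the phase II comparisons are "tested for superiority in favour of intervention versus control treatment period". For the primary outcome, section 5.2.2 says "we will use a Wilcoxon 'signed rank test". Section 3.1 removes every other phase II test: "No statistical comparisons will be done for secondary objectives, only a descriptive analysis will be performed".
- **Fallback analyses.** Section 5.4: "No imputation, only cases available analysis will be done". Section 5.5 (sensitivity analyses) reads None, and section 5.6 rules out additional analyses.
- **Numbers.** Section 2.3 planned 20 analysable patients, later reduced to at most 12 because of production capacity. It reports 9 with complete primary data at the data-blind review.

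**The concern.** Failing to complete a period, or having treatment changed unexpectedly, may be a consequence of the treatment. ICV dopamine may be cut back or stopped because it is not tolerated, and oral treatment may be raised because control is poor. When that happens the patient leaves the efficacy set, and the remaining patients look better on the treatment that lost its failure. A superiority test on the remainder is then biased towards that treatment.

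Blind classification prevents selective labelling, but it does not help when the event being labelled was itself caused by treatment. Listing the excluded patients tells the reader who is missing and leaves the p-value and Hedges' g unchanged. In a set this small, one or two patients can decide the result, and the plan contains nothing that would show whether they did.

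**Working it through.** **1. The plan's own figure.** Inputs from section 2.3: difference 10 PTO points, SD 15, within-patient correlation 0.5, two-sided 0.05.

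- SD of the paired difference = 15 × √(2 × (1 − 0.5)) = 15.
- Paired t power is 78.5% at n = 19 and 80.7% at n = 20, so the stated 20 patients for more than 80% power is reproduced.
- With the same inputs, power of the signed-rank test now planned is about 51% at n = 12 and 36% at n = 9.

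**2. How far excluded patients can move the p-value.** The number randomised is not stated. I assume 1 to 3 excluded patients, because the ceiling of 12 less the 9 analysable leaves at most 3. Let W be the sum of the ranks of the unfavourable differences. The exact two-sided p is 2 × (number of sign patterns with rank sum ≤ W) / 2ⁿ.

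Best case, all 9 favour ICV dopamine: W = 0, p = 2 × 1/512 = 0.0039. Restoring k patients:

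| k | n | W, worst ranks | p | W, smallest unfavourable ranks | p |
|---|---|---|---|---|---|
| 1 | 10 | 10 | 0.084 | 1 | 0.0039 |
| 2 | 11 | 10 + 11 = 21 | 0.32 | 1 + 2 = 3 | 0.0049 |
| 3 | 12 | 10 + 11 + 12 = 33 | 0.68 | 1 + 2 + 3 = 6 | 0.0068 |

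A result in 9 patients that is only just significant (W = 5, p = 0.039) becomes 0.23, 0.58 and 0.97 with 1, 2 or 3 worst ranks added (W = 15, 26, 38).

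**3. False positives when there is no true effect.** Simulated paired differences with mean 0 and SD 15, 12 randomised (assumed). The table gives the chance of a significant result in favour of ICV dopamine.

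| Loss mechanism | False positives for ICV dopamine | Spurious mean benefit (PTO points) |
|---|---|---|
| Unrelated to outcome | about 2% | none |
| Each unfavourable difference lost with probability 0.25 | about 5% | about 1.7 |
| Each unfavourable difference lost with probability 0.5 | about 12% | about 4 |
| The three worst of 12 lost | about 27% | about 6 |

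Dropping only the worst 1 of 10 or the worst 2 of 11 gives about 7% and 16%. The last row is an extreme, because it makes loss depend entirely on outcome. Since the differences are symmetric about zero, the same rates apply against ICV dopamine if the lost patients are those who did badly on placebo.

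**4. Is there another route back into an efficacy test?** The long-term analysis in section 5.2.3 asks about maintenance and, under section 3.3, requires at least 6 months of ICV dopamine after phase II. It cannot recover patients who failed during the crossover.

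**The case against.** The strongest defence has four parts.

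- **Not every change excludes.** Section 3.2 is limited to *unexpected* modifications, and the protocol may say which changes are expected. A patient who does badly but completes both periods without such a change stays in the test. This stands: a reader might infer that any dose or oral-treatment change removes a patient, and the text does not say so.
- **The direction is not fixed.** The same rule removes patients who do badly on placebo and have oral treatment raised unexpectedly. A reader might infer that the bias must favour ICV dopamine. The SAP does not support that either.
- **Early intolerance is partly screened out.** Sections 2.1 and 2.2 admit to phase II only patients who finished titration without complications. This makes heavy outcome-related loss less plausible and the milder rows of the table more so. It does not exclude loss during the 4-week periods.
- **The plan is open about what it does.** It calls the study a proof of concept, relies on effect size and individual plots as well as the test, explains exclusions and withdrawals, and keeps dosed patients in the safety population. With about a dozen patients, readers will see who is missing. That helps interpretation, but the plan still reports one test at the 5% level and one effect size, both on the selected set only.

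It is also tempting to say that the 9 will shrink once major deviators are removed. Section 2.3 says that the 9 have complete data and could be analysed, and deviations are classified in blind review, so the 9 may already exclude deviators.

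**Conclusion.** The point holds as a risk that the plan leaves open. Bias has not been shown. The sole phase II superiority test uses a completer set without major deviations, both exclusion routes can follow from treatment, and no efficacy analysis retains the excluded patients.

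The actual size cannot be computed, because the SAP states neither how many patients were randomised nor why only 9 have complete data. If the losses are unrelated to treatment, there is no bias. If 1 to 3 failures on ICV dopamine were lost, even a unanimous result in 9 patients (p = 0.004) could become 0.084 to 0.68; if the lost patients were only slightly unfavourable, it would stay at or below 0.007. Under no effect, the one-directional false-positive rate runs from about 2% to 27% across the mechanisms examined, with 5% to 12% for moderate outcome-related loss. These figures rest on the assumed 12 randomised, normal differences and the SAP's SD of 15.

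**What to change.** 1. **Section 3.3.** Define the primary phase II efficacy set as all randomised patients with PTO in both periods, whatever their deviations, analysed by randomised sequence. Keep the current definition as a supportive per-protocol set.
2. **Section 5.5.** The first change alone still omits non-completers and may leave the same 9 patients. Replace the entry None with a worst-rank signed-rank analysis. Each randomised patient who lacks a PTO value because of intolerance or lack of effect gets the worst rank against the treatment being taken at the time, whether ICV dopamine or placebo. Report this p-value beside the main one.
3. **Section 2.3.** State the number randomised, the reason each patient is not among the 9, and whether the 9 already excludes major deviators.

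The cost is SAP wording and one extra run of the same test, with no new data. The downside is some dilution of the treatment contrast from patients whose treatment was modified. The reasons for missing PTO should be assigned before unblinding; if that is no longer possible, label the analysis as post hoc.

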In second efficacy phase II, 20 patients will be enrolled after terminating the titration phase I without complications and randomized in two groups according to cross-over design of 2 treatment periods of 4 weeks separated by a therapeutic switch carried out in the hospital. The previous treatment will be stopped at the end of period 1 and replaced by the new treatment, after 3 weeks of washout. During the 2 treatment periods and washout period, the patients will be treated by oral L-dopa at optimized dose. In summary, patients will be randomized into two groups according to the following treatment sequences:

- group 1 (n=10): period 1(ICV dopamine treatment + oral L-dopa at optimized dose) vs. period 2 (oral treatment at optimized dose + ICV Placebo treatment)
- group 2 (n=10): period 1: (oral treatment optimized + ICV Placebo treatment) vs. period 2 (ICV dopamine treatment + oral L-dopa at optimized dose)

At the end of phase II, all patients are invited to continue to use ICV dopamine treatment over the long term with the dose that allows satisfactory motor control (less than 1 hour of moderate or severe off per day and less than half an hour of dyskinesia) with or without a minimal residual dose of oral dopaminergic therapy.

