#### ***Secondary outcomes of efficacy:***

- Patient diary measures
  - Time in good autonomy is expressed in % is the percentage of time in On state or with slight dyskinesia or slight off.
  - Time in perfect control is expressed in % or in hours (h) and represents the time in On state without dyskinesia
  - Time in “on” time without troublesome dyskinesia is expressed in % and represents the Time On with or without slight dyskinesia
  - Time in “on” time without dyskinesia and/or with slight dyskinesia and/or with slight bradykinesia is expressed in %
  - Time in dyskinesia is expressed in % and represents the time with slight, moderate or severe dyskinesia
  - Time in severe dyskinesia (%)
  - Time in severe bradykinesia = Time in severe off (%)
- Clinical criteria at end of study treatment period (V2 for first sequence treatment and V4 for second sequence treatment)
  - MDS-UPDRS parts II, III and IV

- The abnormal Involuntary Movement Score (AIMS) and the Dyskinesia rating scale (DRS) score

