***Secondary outcomes of safety:***

- MDS-UPDRS parts I
- Epworth Sleepiness Scale and Parkinson's Disease Sleep Scale
- Cognitive measures (MOCA, NPI, PAS, LARS and ECMP)
- Psychiatric tolerance: a score from a simple questioning on the disorders (no thymic, anxious, psychotic decompensation).
- Frequency of adverse events during the 4 weeks of treatment period reported by the patient and/or noted by the investigator according to clinical examination, ECG, blood pressure, pulse and biological assessment (standard biology, biological iron assessment, blood and urinary levels of dopamine and its metabolites (HVA and 5-cysteinyl-dopamine) and variations in weight, temperature, and blood pressure on the orthostatic hypotension test.

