***Secondary outcomes:***

For secondary and exploratory quantitative outcomes, only a descriptive analysis will be done by reporting the mean, median and range values as well as plotting the values using spaghetti plots showing the change from control to experimental period (by indicated the sequence of treatment using dedicated colors). We will also report the standardized differences (Hedges'g) calculated from the within-patient's differences (E1-S2 and E2-S1) as effect size (calculated on rank transformed data). The frequency of adverse events during the 4 weeks of treatment period will be reported in each treatment group without statistical comparison.

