***Secondary outcomes:***

The same methods described to analyse the primary outcome of long-term follow-up phase will be used to analyse secondary and exploratory quantitative outcomes.

The frequency of adverse events from end of phase II trial to the last available follow-up will be reported.

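### The long-term phase has one analysis set, conditional on 6 months of ICV dopamine, and no safety set; separately, the washout is in no stated adverse-event summary and two long-term adverse-event windows conflict

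*SAP*

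**What the plan says.** **Population.** SAP section 3.3 gives phase I a safety set of all operated patients, dosed or not. Phase II has an efficacy set and a safety set of all randomised patients who receive ICV dopamine or placebo. The long-term phase has one set only: "all patients having received ICV dopamine for at least 6 months after end of the phase II part will included in the analysis population". Section 2.1 states who may enter that phase: "all patients are invited to continue to use ICV dopamine treatment over the long term". Section 1.3 sets its objectives as maintenance of efficacy and of tolerance. Sections 5.4 and 5.5 plan available-case analysis and no sensitivity analysis.

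**Phase II adverse events.** Section 5.2.2 says: "The frequency of adverse events during the 4 weeks of treatment period will be reported in each treatment group without statistical comparison". Section 5.1.2 uses the same 4-week window. On the switch between periods, section 2.1 says: "The previous treatment will be stopped at the end of period 1 and replaced by the new treatment, after 3 weeks of washout".

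**Long-term adverse events.** The outcome definition in 5.1.3 reads: "Frequency of adverse events during the 4 weeks of treatment period reported by the patient". The analysis text in 5.2.3 reads: "The frequency of adverse events from end of phase II trial to the last available follow-up will be reported".

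**Long-term clinical scales.** Section 5.1.3 places them as follows: "Clinical criteria at end of study treatment period (V2 for first sequence treatment and V4 for second sequence treatment". Table 1 schedules long-term visits every 6 months.

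**The concern.** Staying on ICV dopamine for 6 months is itself a result of tolerance and efficacy. A patient who stops at month 3 because of harm or lost effect is the kind of failure that the long-term objectives are meant to detect, yet the population rule excludes that patient. Since there is no long-term safety set, the rule governs the adverse-event frequency as well as the maintenance estimate. Both results would then describe only those who did well enough to continue.

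Two reporting gaps stand apart from this. Events in the washout, which includes the weeks just after ICV dopamine is stopped in the dopamine-first sequence, belong to no stated summary. The long-term adverse-event outcome also has two incompatible windows, so two analysts could produce different tables from the same data.

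**Working it through.** The plan gives no figure on this point, so there is none to reproduce. The check sets its rules side by side and adds a short illustration.

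**1. Where a patient who stops at month 3 of the long-term phase is counted**

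| Analysis | Counted? | Source |
|---|---|---|
| Phase I and phase II safety sets | Yes, but only for events in those phases | 3.3 |
| Long-term maintenance estimate | No, under 6 months of treatment | 3.3, 5.2.3 |
| Long-term adverse-event frequency | No, if the only defined long-term set applies; 5.2.3 names no other | 3.3, 5.2.3 |
| Withdrawal disposition | Yes, if the patient also leaves follow-up | 4.3 |

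The levels listed in 4.3 are consent withdrawal (two kinds), loss to follow-up and investigator decision. A patient who stops ICV dopamine but stays in follow-up fits none of them clearly.

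**2. Size for adverse events (illustration)**

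The SAP gives neither the number entering the long-term phase nor the number stopping early. Assume N = 9 (patients with complete phase II primary data, section 2.3) or N = 12 (the revised sample size, section 2.3). Let k patients stop before 6 months, each with an event, and let nobody else have one. The proportion is k/N if everyone is counted and 0/(N − k) under the 6-month set.

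| N | k | All who continued | 6-month set |
|---|---|---|---|
| 9 | 1 | 1/9 = 11% | 0/8 |
| 9 | 2 | 2/9 = 22% (exact 95% CI 3% to 60%) | 0/7 |
| 9 | 3 | 3/9 = 33% | 0/6 |
| 12 | 1 | 1/12 = 8% | 0/11 |
| 12 | 2 | 2/12 = 17% | 0/10 |
| 12 | 3 | 3/12 = 25% | 0/9 |

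Each omitted early stopper with an event therefore costs 1/12 to 1/9, about 8 to 11 points. If patients who stay on treatment also have events, the loss is smaller. With N = 9, three patients with events and one of them an early stopper, the proportion falls from 3/9 = 33% to 2/8 = 25%, or 8 points.

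**3. Adverse-event windows**

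The phase II schedule is 4 + 3 + 4 = 11 weeks. The stated windows cover the two 4-week periods, and the long-term window opens at the end of phase II. The washout is left out: 3/11 = 27% of the scheduled weeks. Table 1 collects adverse events at every visit, so the gap lies in reporting and not in collection.

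**4. Long-term wording**

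Section 5.1.3 allows 4 weeks for long-term adverse events; 5.2.3 runs from the end of phase II to the last available follow-up. Both cannot define the same outcome. V2 and V4, named in 5.1.3 for the clinical scales, are the ends of the two phase II periods (5.1.2).

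**The case against.** The 6-month rule has a rationale. The first scheduled long-term visit is at 6 months, so an earlier stopper may have no long-term efficacy value to compare with phase II. This stands for the change-from-phase-II estimate, and the set can be kept for that purpose. It does not justify using the set for adverse events.

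Section 5.2.3 names no population, so the loss of early stoppers' events is an inference from 3.3 and not a stated rule. That is correct. However, 3.3 offers no other long-term set, and if all continuing patients were meant, the plan should say so.

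Washout events belong to neither treatment unambiguously, so leaving them out of a by-treatment table is defensible. This also stands, but a separate summary is still needed.

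A reader might infer more than the SAP supports:

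- *That early stoppers appear nowhere.* Withdrawals are reported with timing and reason (4.3), and patients who stop during phase I or II remain in the safety sets of those phases.
- *That the washout gap causes the loss of long-term stoppers.* The washout comes before the long-term phase and affects crossover patients; the two gaps are independent.
- *That the long-term clinical scales would contain no long-term data.* Table 1 schedules the MDS-UPDRS and dyskinesia scales at the six-monthly visits, and 5.2.3 compares the last available follow-up with phase II. V2 and V4 can be read as the phase II reference. This is a minor wording matter.
- *That a maintenance proportion shifts by 8 to 11 points.* The SAP defines no such proportion. The long-term primary outcome is a continuous percentage of time analysed by a mixed model.

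**Conclusion.** The point holds in this form. The only long-term set is conditional on an outcome that occurs after entry, and nothing in the plan offsets that selection. To the extent that early stopping reflects harm or lost effect, reported tolerance and maintenance will be biased in favour of ICV dopamine. The bias in the maintenance estimate cannot be sized from the document. For adverse events, the figure of 8 to 11 points per omitted patient rests on three assumptions: 9 to 12 entrants, an event in the omitted patient, and no events in the others. Whether anyone stops early is not known from the SAP.

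The washout omission and the conflict between 5.1.3 and 5.2.3 follow directly from the text and need no assumption. All three matters should be corrected before the analyses they affect.

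**What to change.** 1. **Long-term sets (3.3, 5.2.3).** Define a long-term safety set of every patient who receives any ICV dopamine after the end of phase II, and report adverse events from that point for all of them. Keep the 6-month set only for the change-from-phase-II estimate. Beside that estimate, show how many patients stopped earlier, when and why.
2. **Washout (5.1.2, 5.2.2).** Report washout adverse events as a separate interval, by preceding treatment.
3. **Wording of 5.1.3.** Reconcile the 4-week adverse-event window with the window in 5.2.3. As a minor correction, reconcile the V2/V4 wording for the clinical scales, under both the secondary efficacy and the exploratory outcomes, with the six-monthly visits in Table 1.

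The cost is SAP wording and slightly more tabulation. Adverse events are already collected at every visit. The safety and maintenance figures may look less favourable.
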